7.1 Allowed Medications and Treatments

Standard therapy for COVID-19 is allowed except for treatments noted in the exclusion criteria described above and as noted in the prohibited medications section below.

Prohibited Medications and Treatments: ANTICOAGULANT/ANTIPLATELET DRUGS, CNS DEPRESSANTS, CYCLOSPORINE, IMMUNOSUPPRESSANTS

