SUBJECT SELECTION CRITERIA	 Inclusion Criteria: Patients with mild COVID19 (defined as upper respiratory tract infection symptoms in the absence of clinical or radiological signs of pneumonia). -Adult (18 - 65 years old). Written informed consent by the patient (or legally authorized representative) prior to initiation of any study procedures. -All patients should understand and agree to comply with planned study procedures. Polymerase chain reaction (PCR)-confirmed infection with Severe Acute Respiratory Syndrome Coronavirus-2 (SARS-CoV-2). Exclusion Criteria:
	Patients with pneumonia or severe illness requiring admission to intensive care unit.Asymptomatic patients.

TEST PRODUCT,	 -Severe chronic kidney disease (i.e. estimated glomerular filtration rate [eGFR] < 30 mL/min) or end stage renal disease requiring dialysis -Severe chronic liver disease (Alanine transaminase [AIT] or Aspartate transaminase [AST] > 5 times the upper limit of normal). -Pregnancy or breast feeding. -Anticipated transfer within 72 hours to another hospital that is not a study site. -Allergy to the study medication. SFDA-licensed Marnys CUMINMAR Nigella sativa oil 500mg softgel cansules in oral twice daily dose for 10 days.
OF ADMINISTRATION	
CONTROL PRODUCT, DOSE AND ROUTE OF ADMINISTRATION	NA
DURATION OF SUBJECT PARTICIPATION AND DURATION OF STUDY	Subjects will be on study for up to 14 days Screening: up to 7 days Treatment: 10 days Follow-up: 14 days The total duration of the study is expected to be 12 months
CONCOMMITANT MEDICATIONS	Allowed: Any medication with no interaction with NS Prohibited: ANTICOAGULANT/ANTIPLATELET DRUGS, CNS DEPRESSANTS, CYCLOSPORINE, IMMUNOSUPPRESSANTS
EFFICACY EVALUATIONS	Clinical monitoring for 14 days
PRIMARY ENDPOINT	Proportion of patients who clinically recovered (defined as 3 days of no symptoms) within 14 days after date of onset of symptoms.
SECONDARY ENDPOINTS	 Improvement of Clinical Parameters: o Time to full clinical recovery o Time to progression to pneumonia or hypoxia o Duration of illness o Discharge to home o Normalization of chest radiograph. o Rate of complications: ICU admission, noninvasive ventilator, superadded infection

	o Death.
	- Normalization of Routine Laboratory Tests:
	o Complete Blood Count (CBC)
	o Erythrocyte sedimentation rate (ESR)
	o C-reactive protein
	o D-dimer
	o Liver function test
	o Renal function test
	o Lactate Dehydrogenase (LDH),
	o Immunoglobulins (IgA, IgE, IgG, IgM),

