4 STUDY DESIGN

4.1 Study Overview

This is a single center, open-label, controlled, randomized, phase II clinical trial. 200 of subjects are planned. Each subject will be administered a single dose (500 mg) of study drug twice daily for 10 days. Subjects will be assigned to the treatments in random order. Evaluations will be taken daily for evaluationg symptoms imrovpment.

Screening data will be reviewed to determine subject eligibility. Subjects who meet all inclusion criteria and none of the exclusion criteria will be entered into the study.

The following treatment regimens will be used:

- Experimental treatment NS at the following dose 500 mg twice daily
- Comparator Standard care for COVID-19

Total duration of subject participation will be 14 days. Total duration of the study is expected to be 12 months.

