6.3 Exclusion Criteria

-Patients with pneumonia or severe illness requiring admission to intensive care unit. -Asymptomatic patients.

-Severe chronic kidney disease (i.e. estimated glomerular filtration rate [eGFR] < 30 mL/min) or end stage renal disease requiring dialysis

-Severe chronic liver disease (Alanine transaminase [AIT] or Aspartate transaminase [AST] > 5 times the upper limit of normal).

-Pregnancy or breast feeding.

-Anticipated transfer within 72 hours to another hospital that is not a study site.

-Allergy to the study medication.

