7 CONCURRENT MEDICATIONS

All subjects should be maintained on the same medications throughout the entire study period, as medically feasible, with no introduction of new chronic therapies.

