9.1 Clinical Assessments

9.1.1 Concomitant Medications

All concomitant medication and concurrent therapies will be documented at Baseline/Screening and at Study Days and at early termination when applicable. Dose,

route, unit frequency of administration, and indication for administration and dates of medication will be captured.

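### Four drug groups are prohibited, but current users are not excluded, so a patient on a barred drug is eligible and can be dispensed Nigella sativa (NS)

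*Combined protocol and SAP*

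**What the plan says.** The prohibition appears in Section 7.1, "Prohibited Medications and Treatments: ANTICOAGULANT/ANTIPLATELET DRUGS, CNS DEPRESSANTS, CYCLOSPORINE, IMMUNOSUPPRESSANTS", and again in the synopsis. There it is paired with an allowance for "Any medication with no interaction with NS", so the list reads as an interaction safeguard. Section 7.1 also says "Standard therapy for COVID-19 is allowed except for treatments noted in the exclusion criteria described above".

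The entry rule is in Section 4.1: "Screening data will be reviewed to determine subject eligibility", followed by "Subjects who meet all inclusion criteria and none of the exclusion criteria will be entered into the study". The exclusion list in 6.3 covers disease severity, absence of symptoms, kidney and liver disease, pregnancy or breast feeding, expected transfer, and "Allergy to the study medication". That last item is the only one about a medicine. Section 6.2 names no concurrent drug, and no wash-out is described anywhere.

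For drugs already being taken, the opening of Section 7 says "All subjects should be maintained on the same medications throughout the entire study period, as medically feasible". Section 9.1.1 says "All concomitant medication and concurrent therapies will be documented at Baseline/Screening and at Study Days". The Visit 1 list in 10.1 puts the recording of concomitant medications at step 5, randomisation at step 6 and dispensing at step 7.

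Section 13 counts use of a prohibited medication as a protocol violation and leaves any withdrawal to the sponsor. Section 12.1 allows study treatment to be stopped in the subject's interest, or for a violation that requires it.

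**The concern.** A prohibited-medication list protects patients only if it is applied before the first dose. Here the rules that decide who enters, and what they go on taking, make no reference to it. Staff who follow the entry and continuation rules literally can give NS to someone on a drug that the protocol says must not be combined with it. The information needed to prevent this is already on the form when the capsules are handed over.

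What is at stake is mainly patient safety, and then consistency. The same patient is correctly enrolled under one section and in violation under another, and two investigators could reasonably handle that patient differently.

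**Working it through.** No figure in the plan bears on this point, so the check follows one hypothetical patient through the text: an adult with mild, PCR-confirmed COVID-19 who takes an antiplatelet drug and meets no criterion in 6.3.

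1. **Eligibility (6.2, 6.3).** No inclusion criterion fails and no exclusion criterion applies. The patient is eligible.
2. **Entry (4.1).** Entry depends on those two lists alone. The screening review is a review against them, so the patient is entered.
3. **Existing medication (Section 7).** The default is to continue. The feasibility qualifier permits a change but does not require one.
4. **Visit 1 (10.1).** The antiplatelet drug is recorded at step 5. Steps 6 and 7 follow with no condition attached. If allocated to NS, the patient receives it.
5. **Status (7.1, 13).** The patient is now using a prohibited medication and is a violator from the first dose. A control patient on the same drug is also a violator, although no NS is given.
6. **Consequence (12.1, 13).** Treatment may be stopped on judgement, and the sponsor decides on withdrawal. No criterion is given for either, and both come after dispensing.

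At no step is staff told to stop the antiplatelet drug, withhold NS or refuse entry.

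Could the prohibition be read as an exclusion in its own right? Section 13 lists failure to meet the inclusion or exclusion criteria, and use of a prohibited medication, as two separate violations. The protocol therefore treats them as different things, and 4.1 ties entry only to the first.

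**The case against.** The best reply is that the protocol is not silent. The prohibited list sits inside Section 7, and a specific ban would normally override a general sentence about staying on the same drugs. The synopsis allows only drugs that do not interact with NS. Section 6.2 asks patients to agree to comply with study procedures. Medications are recorded before dispensing, and 12.1 lets the investigator stop treatment at any time.

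Much of this stands. A careful investigator could notice the conflict and act, so co-administration is possible but not inevitable. What does not stand is that the conflict is resolved. Even if the ban overrides continuation, the text does not say whether the patient stops the drug or stays out of the trial. Stopping an anticoagulant or immunosuppressant in order to take a supplement carries its own risk. The compliance wording in 6.2 is not about drugs, and 12.1 operates only after treatment has begun.

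A reader might infer three stronger points, none of which the documents support.

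- *That the 7.1 reference to the exclusion criteria is empty.* Section 6.3 does name dialysis, which is a treatment. The reference is loose, and it names none of the four barred groups, but it is not void.
- *That a definite number of NS patients would be exposed.* The documents give no prevalence of use. Any assumed share p gives 100 × p users among the 100 NS patients only if every user is enrolled and dispensed NS. That is an upper bound on an unsourced figure. With no interaction rate or severity given, it would not measure harm either.
- *That replacing withdrawn users under 12.4 biases the recovery comparison.* That needs replacements to be non-users, yet nothing keeps users out. If replacement continues from the same pool until there are 100 non-users, the NS arm has 100/(1 − p) patients, of whom 100p/(1 − p) are users. The user share is [100p/(1 − p)] ÷ [100/(1 − p)] = p, the same as expected in controls. Section 14.1 keeps dosed subjects in the analysis, and 12.1 encourages those who stop treatment to complete their visits.

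**Conclusion.** The point holds as a safety and consistency defect. The written entry and continuation rules conflict with the protocol's own interaction ban. Followed as they stand, they allow NS to be dispensed to a current user of a barred drug, who is then a violator with only discretionary handling.

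This conclusion rests on the text and on no numerical assumption. The number affected cannot be estimated from the documents, and no efficacy bias is claimed. The defect does not undermine the trial's comparison, but it is more than a missing detail: it concerns avoidable exposure that the protocol itself set out to prevent. It should be corrected.

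**What to change.** Three edits are enough.

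- **6.3:** add *current use of any drug on the 7.1 prohibited list*, checked against the 9.1.1 medication record before randomisation.
- **Section 7:** change the continuation rule to refer to *the same permitted medications*.
- **7.1:** add a sentence saying that if a barred drug becomes necessary after randomisation, NS is stopped and the 14-day follow-up is completed.

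The 6.3 check needs no new data or visit, because medications are already recorded before randomisation. The exclusion applies before allocation and so affects both arms alike. The cost is the loss of recruits who use a barred drug. Their share is not given in the documents, but the protocol already says they should not take these drugs on study.

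Two possible extensions are left out. Excluding patients expected to need a barred drug would add a prospective judgement that 9.1.1 does not record. The replacement rule (12.4) and the analysis set (14.1) raise separate questions that this correction does not depend on.

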8 STUDY TREATMENTS

8.1 Method of Assigning Subjects to Treatment Groups

Up to 200 eligible patients will be randomly assigned to treatment or control groups in a 1:1 ratio using a computer-generated randomization scheme developed by http://www.randomization.com.

8.2 Blinding

NA

8.3 Formulation of Test and Control Products

SFDA-licensed Marnys CUMINMAR Nigella sativa oil 500mg softgel oral capsules.

No control product will be used.

8.3.1 Packaging and Labeling

Packaging: Study drug is supplied in cartons containing 3 strips of 20 single dose each. Each patient will receive 1 strip (20 single dose).

Labeling example: Each strip study drug will be labeled with the required SFDA statement, the protocol number, a treatment number, the name of the sponsors, and directions for patient use and storage.

8.4 Supply of Study Drug at the Site

The Sponsor will ship Study Drug to the investigational sites. The initial study drug shipment will be shipped after site activation (i.e., all required regulatory documentation

has been received by the Sponsor and a contract has been executed). Subsequent study drug shipments will be made after site request for resupply.

8.4.1 Dosage/Dosage Regimen

Nigella sativa oil 500mg softgel capsules in oral twice daily dose for 10 days

8.4.2 Dispensing

The investigator will dispense the drug at the participation site

8.4.3 Administration Instructions

Take 1 capsule with plenty glass of water.

8.5 Supply of Study Drug at the Site

the study drug will be delivered from the supplier to the investigational site.

8.5.1 Storage

Study drug should be stored by the study site at controlled room temperature, 15 to 25°C in a dry place away from light. If the temperature of study drug storage in the clinic/pharmacy exceeds or falls below this range, this should be reported to the Sponsor or designee and captured as a deviation. Subjects will be instructed to store the medication in original packaging at room temperature according to the instructions outlined on the Drug Administration Instructions.

8.6 Study Drug Accountability

An accurate and current accounting of the dispensing and return of study drug for each subject will be maintained on an ongoing basis by the investigator.

8.7 Measures of Treatment Compliance

Subjects will be monitored on daily bases during the study period for their study drug intake and any adverse events.

9 STUDY PROCEDURES AND GUIDELINES

A Schedule of Events representing the required testing procedures to be performed for the duration of the study is diagrammed in Appendix 1.

Prior to conducting any study-related activities, informed consent will be taken by the subject or subject's legal representative. If appropriate, assent must also be obtained prior to conducting any study-related activities.

9.1 Clinical Assessments

9.1.1 Concomitant Medications

All concomitant medication and concurrent therapies will be documented at Baseline/Screening and at Study Days and at early termination when applicable. Dose,

route, unit frequency of administration, and indication for administration and dates of medication will be captured.

9.1.2 Demographics

Demographic information (date of birth, gender, race) will be recorded at Screening.

9.1.3 Medical History

Relevant medical history, including history of current disease, other pertinent respiratory history, and information regarding underlying diseases will be recorded at Screening.

9.1.4 Physical Examination

A complete physical examination will be performed by either the physician of the research team at study site. Qualified staff (MD, NP, RN, and PA) may complete the abbreviated physical exam at all other visits. New abnormal physical exam findings must be documented and will be followed by a physician or other qualified staff.

9.1.5 Adverse Events

Information regarding occurrence of adverse events will be captured throughout the study. Duration (start and stop dates and times), severity/grade, outcome, treatment and relation to study drug will be recorded on the case report form (CRF).

9.2 Clinical Laboratory Measurements

NA

10 EVALUATIONS BY VISIT

10.1 Visit 1 (Day 1)

- 1. Review the study with the subject (subject's legal representative) and obtain written informed consent.
- 2. Assign the subject a unique screening number.
- 3. Record demographics data.
- 4. Record medical history, diagnosis date.
- 5. Record concomitant medications.
- 6. Randomize subject,
- 7. Dispense study drug,
- 8. Initiate subject diary in CRF.

10.2 14 days monitoring

- 1. Record patients' symptoms
- 2. Record any Adverse Experiences and dosing compliance.
- 3. Concomitant medications review.

11 ADVERSE EXPERIENCE REPORTING AND DOCUMENTATION

11.1 Adverse Events

An adverse event (AE) is any untoward medical occurrence in a clinical investigation of a patient administered a pharmaceutical product and that does not necessarily have a causal relationship with the treatment. An AE is therefore any unfavorable and unintended sign (including an abnormal laboratory finding), symptom or disease temporally associated with the administration of an investigational product, whether or not related to that investigational product. An unexpected AE is one of a type not identified in nature, severity, or frequency in the current Investigator's Brochure or of greater severity or frequency than expected based on the information in the Investigator's Brochure.

The Investigator will probe, via discussion with the subject, for the occurrence of AEs during each subject visit and record the information in the site's source documents. Adverse events will be recorded in the patient CRF. Adverse events will be described by duration (start and stop dates and times), severity, outcome, treatment and relation to study drug, or if unrelated, the cause.

AE Severity

The National Cancer Institute's Common Terminology Criteria for Adverse Events (CTCAE) Version 3.0 should be used to assess and grade AE severity, including laboratory abnormalities judged to be clinically significant. The modified criteria can be found in the study manual. If the experience is not covered in the modified criteria, the guidelines shown in Table 1 below should be used to grade severity. It should be pointed out that the term "severe" is a measure of intensity and that a severe AE is not necessarily serious.

Severity (Toxicity Grade)	Description
Mild (1)	Transient or mild discomfort; no limitation in activity; no medical intervention or therapy required. The subject may be aware of the sign or symptom but tolerates it reasonably well.
Moderate (2)	Mild to moderate limitation in activity, no or minimal medical intervention/therapy required.
Severe (3)	Marked limitation in activity, medical intervention/therapy required, hospitalizations possible.
Life-threatening (4)	The subject is at risk of death due to the adverse experience as it occurred. This does not refer to an experience that hypothetically might have caused death if it were more severe.

Table 1.	AE Severity Grading	
I abit I.	The bevenity of adding	

AE Relationship to Study Drug

The relationship of an AE to the study drug should be assessed using the following the guidelines in Table 2.

Relationship to Drug	Comment
Definitely	Previously known toxicity of agent; or an event that follows a reasonable temporal sequence from administration of the drug; that follows a known or expected response pattern to the suspected drug; that is confirmed by stopping or reducing the dosage of the drug; and that is not explained by any other reasonable hypothesis.
Probably	An event that follows a reasonable temporal sequence from administration of the drug; that follows a known or expected response pattern to the suspected drug; that is confirmed by stopping or reducing the dosage of the drug; and that is unlikely to be explained by the known characteristics of the subject's clinical state or by other interventions.
Possibly	An event that follows a reasonable temporal sequence from administration of the drug; that follows a known or expected response pattern to that suspected drug; but that could readily have been produced by a number of other factors.
Unrelated	An event that can be determined with certainty to have no relationship to the study drug.

Table 2. AE Relationship to Study Drug

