5.3 Safety Evaluations

Incidence of adverse events from the investigational drug or transfer to ICU

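### Table 2's causality categories leave two kinds of adverse event without a home, so a safety measure limited to drug-caused events depends on the rater

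*Combined protocol and SAP*

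**What the plan says.** Section 11.1, Table 2, defines four categories and introduces them as guidelines:

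- **Definitely** has two limbs, joined by an or: "Previously known toxicity of agent; or an event that follows a reasonable temporal sequence from administration of the drug". The second limb goes on to require an event "that follows a known or expected response pattern to the suspected drug; that is confirmed by stopping or reducing the dosage of the drug", with no other reasonable explanation.
- **Probably** repeats the timing, pattern and stopping conditions, and asks that the subject's clinical state or other interventions be an unlikely explanation.
- **Possibly** requires plausible timing and an event "that follows a known or expected response pattern to that suspected drug; but that could readily have been produced by a number of other factors".
- The last, **Unrelated**, is "An event that can be determined with certainty to have no relationship to the study drug".

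The same section foresees events outside the known profile: "An unexpected AE is one of a type not identified in nature, severity, or frequency in the current Investigator's Brochure". It extends the term to events of greater severity or frequency than the Brochure leads one to expect. For each event the CRF is to hold "severity, outcome, treatment and relation to study drug, or if unrelated, the cause".

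Section 5.3 and the synopsis give the safety measure as "Incidence of adverse events from the investigational drug or transfer to ICU". Neither says which Table 2 categories meet its first part. Section 14 covers data sets, baseline variables, the two efficacy analyses and sample size. It describes no tabulation of adverse events.

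**The concern.** A causality scale should give every event a place. This one sets a high bar at both ends and leaves a space between. All routes to a related score pass through prior knowledge of the product's effects, while the only other score demands certainty. There is no category for an unlikely or unassessable relationship.

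The space is not exotic in this trial. Every participant has symptomatic COVID-19 (Sections 6.2 and 6.3), so another possible cause is nearly always present and certainty of no relationship will be rare. The background and risk sections list no known reactions to the product, so the protocol itself gives raters nothing against which to judge a known pattern. The Investigator's Brochure is mentioned but is not part of the documents.

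At stake is what the stated safety measure counts. If it rests on attribution and the attribution scale has gaps, two careful investigators can score the same event differently. A reaction not previously described is the one most exposed. The trial is also open-label, so the arm is known when the score is given.

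**Working it through.** The plan gives no figure to reproduce. The check is whether the four definitions cover all events. I coded each as conditions:

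| Category | Plausible timing | Known or expected pattern | Confirmed on stopping or reducing | Other cause |
|---|---|---|---|---|
| Definitely, limb 1 | not required | previously known toxicity alone suffices | not required | not required |
| Definitely, limb 2 | yes | yes | yes | none |
| Probably | yes | yes | yes | none or unlikely |
| Possibly | yes | yes | not required | readily available |
| Unrelated | certainty of no relationship | | | |

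Take events that are neither a previously known toxicity nor certainly unrelated. Limb 1 and Unrelated are then closed. The remaining combinations number 2 (timing) × 2 (pattern) × 2 (confirmation) × 3 (other cause: none, unlikely, readily available) = 24.

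- **Plausible timing, known pattern:** 2 × 3 = 6 combinations. Three are confirmed on stopping, and all three fit a category. Of the three not confirmed, only the one with a readily available other cause fits (Possibly). So 4 fit and 2 do not.
- **Plausible timing, no known pattern:** 2 × 3 = 6 combinations. None fits, because limb 2, Probably and Possibly all need the pattern.
- **No plausible timing:** 2 × 2 × 3 = 12 combinations. None fits, because the same three definitions need timing.

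Among plausibly timed events, 6 + 2 = 8 of 12 combinations have no category. Over all 24, the number is 12 + 6 + 2 = 20. These are counts of logical combinations. They are not weighted by how often each would occur and say nothing about expected numbers of events.

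One further reading of the table: limb 1 of Definitely, taken literally, is met by any known toxicity whatever its timing and whatever else could explain it. That errs in the opposite direction, towards over-attribution.

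Set beside Section 5.3, the consequence follows. The measure asks for events from the drug, no text maps that phrase to Table 2, and the 8 plausibly timed combinations have no score to map.

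**The case against.** The best case against is that little is lost. Adverse events are recorded on the CRF whatever their cause (Sections 9.1.5 and 11.1). SAEs are documented whether or not related (11.2.1) and go to the ethics committee regardless of causality (16.2). Unanticipated problems involving risk go promptly to the IRB and sponsor (16.5, item 8). The synopsis plans a safety review by an independent committee at about half of completions, with no stated limit to related events. ICU transfer counts without attribution. All of this stands: the exposure is in the attribution-based measure, not in the record.

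Several stronger readings are tempting and are not supported:

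- **That unclassifiable events will be entered as Unrelated.** The documents do not say so. Unrelated demands certainty and a stated cause, which both discourage that entry. Because the table is guidance, a rater may take the nearest fit, which for a plausibly timed event with COVID-19 as another explanation is arguably Possibly. What can be supported is rater dependence.
- **That the causality field decides the endpoint.** This is an inference, since 5.3 does not refer to Table 2.
- **That every unexpected event falls in the gap.** Section 11.1 also calls an event unexpected when a known type is more severe or frequent than expected. Such an event can follow a known pattern and still be scored.
- **That events after the last dose drop out because stopping cannot confirm them.** If dosing starts on Day 1, that concerns onset on about 14 − 10 = 4 days of monitoring. With a known pattern and a ready alternative cause, Possibly still applies. If Possibly counts as related, losing Probably changes nothing. Only known-pattern events without a ready alternative are stranded.

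**Conclusion.** The gap is real on a literal reading. Table 2 has no category for a plausibly timed event with no known or expected pattern and no certainty of being unrelated. It has none either for a known-pattern event that is not an established toxicity, lacks confirmation on stopping or reducing the drug, and has no ready alternative cause. The stated safety measure is confined to events from the drug, no rule says which categories count, and no summary of all adverse events is planned. Scoring of these events therefore depends on the rater, and they can be left out of the measure.

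Severity is minor to moderate. A reader might infer systematic loss of new safety signals, but the documents do not show it, given the recording and reporting rules that apply irrespective of cause. The number of events affected cannot be estimated from the documents.

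The conclusion assumes that no default rule stands elsewhere. The contents list Medical Monitoring and a Safety Management Plan after 11.2, and their text is not in the public copy, so the absence is established only for the sections available.

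**What to change.** In Table 2:

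1. Remove the known-pattern condition from Possibly, so that it takes any event with plausible timing whose relationship to the drug cannot be excluded.
2. Add Unlikely, for events without plausible timing where certainty of no relationship is not available.
3. In Probably and Definitely, ask for confirmation on stopping or reducing only where it can be assessed.
4. In Definitely, make a previously known toxicity subject to the timing and alternative-cause conditions as well.

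In Section 5.3, state that Possibly, Probably and Definitely count as related. In Section 14, add a summary of all adverse events by arm regardless of attribution, including controls, who receive no study product.

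Checked against the 24 combinations, the 12 with plausible timing then reach at least Possibly and the 12 without it reach Unlikely, leaving 24 − 12 − 12 = 0 unclassified.

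The cost is the wording of one table, one CRF field, one sentence in 5.3 and one added safety table. No clinical procedure changes. The small downside is that more events will be scored as possibly related. The change is best made before events are scored, since reclassifying later with arms known would be less credible.
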